6.4.7 Subgroup Analyses

The primary efficacy endpoints will be evaluated for subgroups of interest, including:

- Age (< 65 or \geq 65 years)
- Race (White or Non-White)
- Gender
- Iris color (Blue, Brown or Other)

Subgroup summary will be performed using the ITT population for the primary efficacy endpoints only if the number of subjects in a subgroup is appropriate. No statistical comparisons will be conducted.

7. STUDY POPULATION CHARACTERISTICS

7.1 Subject Disposition

Summaries of the number of subjects screened, the number of screen failures and the number of subjects randomized will be produced for all screened subjects.

All randomized subjects will be tabulated by treatment group and study site.

The number in each analysis population (ITT, PP and Safety) will be tabulated by treatment group for all randomized subjects.

The number and percentage of subjects who complete the study and who prematurely discontinue the study, along with the reason for withdrawal, will be tabulated by treatment group for the ITT population.

In addition, the numbers and percentages of subjects who discontinue the study drug before completing the 14-days of dosing and the reason for discontinuing the study drug will be tabulated by treatment group using the Safety population.

Disposition data for all screened subjects will be listed.

7.2 Protocol Deviations

Protocol deviations will be collected in the eCRF. The protocol deviation data will be reviewed for major protocol deviations by the clinical team prior to database lock and unmasking of the study treatment.

The subjects with major protocol deviations including the category of the major protocol deviations will be summarized by treatment group for the ITT population. The number and

percentage of subjects excluded from the PP population and the reason for exclusion will be tabulated by treatment group for the ITT population.

The protocol deviation data will be listed. The data listing will include the type of deviation, the category of the deviation (major/minor), the status of being excluded from the PP population (yes/no) and reason for exclusion.

A data listing of subjects who do not meet the inclusion and exclusion criteria will be provided.

8. DEMOGRAPHICS AND BASELINE CHARACTERISTICS

8.1 Demographics and Baseline Characteristics

Demographic data, including age, age category (< 65 or \geq 65 years), gender, race, ethnicity, iris color, study eye (OD or OS) will be summarized by treatment group and overall.

Demographic and baseline characteristics data, including the data collected on the surgery day (Day 0), will be listed in data listings.

8.2 Medical/Surgical History

General medical and surgical history, and ocular medical and surgical history reported in eCRF will be coded using the Medical Dictionary for Regulatory Activities (MedDRA version 23.1 - September 2020). General medical and surgical history will be summarized by system organ class (SOC) and preferred term for past and current medical conditions separately. Subjects reporting more than one medical condition in a SOC will be counted only once in that SOC. Ocular medical and surgical history will be summarized by SOC and preferred term for the study eye and non-study eye separately.

Data listings of general medical and surgical history, and ocular medical and surgical history will be provided.

8.3 Prior and Concomitant Medications

Prior and concomitant medications, including rescue medications, will be coded using the World Health Organization (WHO) Drug Dictionary (B3 WHO Drug Global - September 2020). When medications cannot be coded, the name entered in the eCRF will be reported.

A summary of concomitant medications taken during the course of the study will be tabulated by Anatomical Therapeutic Chemical (ATC) Classification and WHO drug name. The summary will exclude prior medications with a stop date prior to the date of first dose of the study drug or follow-up medications with a start date after the last day of the study (EOS). Medications used as part of the routine surgical procedure and rescue medications will be summarized separately.

All prior and concomitant medications will be presented in a data listing.

9. TREATMENT COMPLIANCE

Overall treatment compliance per subject for the study eye is defined as:

Treatment compliance (%) = [Total number of doses instilled correctly / (Actual treatment duration) x 2] x100,

where the actual treatment duration is calculated as the number of days between the first dose date and last dose date of study drug.

The treatment compliance will be summarized using descriptive statistics for the Safety population. In addition, the overall treatment compliance will be further categorized as < 80%, 80% – 100% and > 100%, and the number and percentage of subjects with compliance in each category will be presented.

Subject dosing diary data will be listed.

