3.2 Schedule of Events

All assessments including ocular assessments and safety assessments are outlined in Table 2.

Table 2: Schedule of Events

PROCEDURE/ASSESSMENTS ¹	Visit 1 Screening (Day -28 to -1)	Surgery ² Day 0	Visit 2 POD1 ³	Visit 3 POD4 (±1 Day)	Visit 4 POD8 (±1 Day)	Contact POD14	Visit 5 POD15 (+1 Day) ⁴	Visit 6 POD22 (±2 Days) ⁵
ICF, Demography, Medical History	X							
Determine Eligibility, Review Inclusion/Exclusion Criteria	X		X					
Urine pregnancy test only for women of child-bearing potential			X				X	
Ocular Symptoms Assessment ⁶	X		X	X	X		X	X
ETDRS Visual Acuity	X		X	X	X		X	X
Slit Lamp Biomicroscopy ⁷	X		X	X	X		X	X
Indirect Ophthalmoscopy (dilated)	X							X
IOP (Goldmann applanation tonometry) ⁸	X		X	X	X		X	X
Randomization			X					
Dispense Study Drug			X					
Study Drug Dosing BID for 14 days (POD1 to POD14) ⁹			X	X	X	X		
Dispense Diary Card (with instructions for completion)			X	X	X			
Contact Subject ¹⁰						X		
Collect Study Drug							X	
Collect and Check Diary Cards for Accuracy and Compliance				X	X		X	
AEs ⁷ and Concomitant Medications ¹¹	X	X ¹²	X	X	X	X ¹³	X	X

¹ Ophthalmic assessments will be performed in the study eye only at Visits 2-5; and performed on both eyes at Visit 1 (Screening) and at Visit 6 (POD22) or at subject Early Termination/Withdrawal.

² Surgery must occur between one to 28 days after Screening, preferably in the morning. If, due to unexpected events, surgery is postponed and would occur > 28 days past the Screening visit, contact the Study Medical Monitor to determine which, if any, of the screening procedures should be repeated. Subjects will be determined to be a suitable candidate for surgery during a pre-surgery medical assessment, where the routine medication list prescribed by the cataract surgeon should be reviewed to rule out prohibited medications ([protocol Section 5.4.2](#)).

³ Visit 2 (POD1) should be scheduled between 18 to 34 hours following conclusion of surgery on Day 0. All assessments done on POD1 are done prior to Randomization to ensure eligibility. Note: Women-of-childbearing-potential are eligible for enrollment if they have a negative urine pregnancy test on POD1 prior to Randomization and they agree to abstinence from sexual activity or use of highly effective method of contraception.

⁴ Visit 5 (POD15) occurs on the day after the subject completes the study drug administration for 14 days. Women-of-childbearing-potential should have a urine pregnancy test.

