10.2.2.3 Analysis of Endpoint of Rescue Medication Use

The overall number of subjects rescued during the treatment period will be compared between treatment groups using the Pearson Chi-square test. “Rescued during treatment period” is defined as use of rescue medications during the 14-day study drug treatment period. When the treatment

duration of study drug is < 14 days, use of rescue medications will be excluded from the analysis when rescue medications are started > 2 day after the last dose of study drug.

In addition, the cumulative number of subjects rescued at PODs 4, 8, and 15 will be summarized by treatment group and compared between treatment groups using the Pearson Chi-square test at each Analysis Visit. In addition, the number and percentage of subjects rescued in each category of criteria for rescue will be presented for the overall study and at PODs 4, 8, and 15. If multiple rescue medications are used by a subject, only the first time a rescue medication is used will be included in the analysis and summary.

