11.1 Extent of Exposure

Exposure to study drug will be summarized by duration (days) on study drug (the number of days between the first dose date and last dose date of study drug) and total number of doses that are instilled correctly in the study eye using descriptive statistics. In addition, the duration on study drug will be categorized as 1–4 days, 5–8 days, and 9–13 days, and ≥14 days, and the number and percentage of subjects in each category will be presented. The number of doses received per subject will also be categorized as <8 doses, 8–<16 doses, 16–<28 doses, =28 doses, and >28 doses, and the number and percentage of subjects in each category will be presented by treatment group.

If the date of last dose is missing, the date of the last scheduled or unscheduled visit will be used as the date of last dose to calculate the treatment duration.

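### The SAP Section 9 compliance formula puts the factor 2 on the wrong side of the division, and the duration rule omits the +1 that the rest of the SAP implies

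*SAP*

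**What the plan says.** SAP Section 9 defines overall compliance for the study eye as "Treatment compliance (%) = [Total number of doses instilled correctly / (Actual treatment duration) x 2] x100". The duration in that formula has its own rule, given directly below it: "the actual treatment duration is calculated as the number of days between the first dose date and last dose date of study drug". Section 9 then sets three reporting bands: "the overall treatment compliance will be further categorized as < 80%, 80% – 100% and > 100" percent.

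SAP Section 5.2 requires at least 80% compliance for the PP population, as its criterion (iii). SAP Section 10.1.3 lists the PP analysis as the first sensitivity analysis of both primary endpoints.

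SAP Section 11.1 repeats the duration rule for exposure ("the number of days between the first dose date and last dose date of study drug"). There "the duration on study drug will be categorized as 1–4 days, 5–8 days, and 9–13 days, and ≥14 days", and doses received are "categorized as <8 doses, 8–<16 doses, 16–<28 doses, =28 doses, and >28 doses".

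The schedule in SAP Section 3.2 (Table 2) describes the regimen as "Study Drug Dosing BID for 14 days (POD1 to POD14"). SAP Section 10.2.2.3 has a rule for subjects whose treatment "duration of study drug is < 14 days, use of rescue medications will be excluded from the analysis" if started more than two days after the last dose.

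**The concern.** There are two separate defects.

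**The bracket.** The denominator should be the number of doses expected, which is two per day times the days on treatment. The printed parentheses enclose only the duration, so under ordinary order of operations the 2 multiplies the ratio. Every score comes out four times too large.

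**The day count.** The phrase used for duration can mean a date difference or an inclusive count. Section 6.3.4 writes out the +1 when it defines Study Day, but Sections 9 and 11.1 do not. A programmer who subtracts the dates gets 13 days for a full course and 0 for a subject treated on one day only. This version is harder to catch: a score of 107.7% looks plausible in a table that already has a band above 100%, whereas 400% does not.

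The formula decides who enters the PP population, and Section 5.2 requires exclusions to be settled before database lock and unmasking. A looser denominator admits subjects whom the stated 80% rule is meant to exclude.

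**Working it through.** **Inputs.** Two doses a day for 14 days, POD1 to POD14 (SAP Sections 3.1 and 3.2). PP threshold 80% (Section 5.2). Compliance bands below 80%, 80 to 100%, above 100% (Section 9).

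**The plan's own figure.** 2 x 14 = 28 doses, which agrees with the dose band of exactly 28 in Section 11.1.

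**Step 1: formula as printed**, doses / duration x 2 x 100.
- Perfect course, 14 days: 28/14 x 2 x 100 = 400%. With 13 days: 28/13 x 2 x 100 = 430.8%.
- Six doses: 6/14 x 2 x 100 = 85.7%, or 6/13 x 2 x 100 = 92.3%.
- Five doses: 71.4% or 76.9%.

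Six doses are therefore the minimum that reaches 80% under either day count. Six of 28 is a true 21.4%.

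**Step 2: bracket corrected**, doses / (2 x duration) x 100, for a subject first dosed on POD1 and last dosed on POD14.

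| Doses | Inclusive count (2 x 14 = 28) | Date difference (2 x 13 = 26) |
|---|---|---|
| 20 | 71.4% | 76.9% |
| 21 | 75.0% | 80.8% |
| 22 | 78.6% | 84.6% |
| 23 | 82.1% | 88.5% |
| 26 | 92.9% | 100.0% |
| 27 | 96.4% | 103.8% |
| 28 | 100.0% | 107.7% |

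The minimum that meets 80% is 23 doses on the inclusive count and 21 on the date difference. Over all counts from 0 to 28, exactly four change band. Doses of 21 and 22 move from below 80% to 80-100% and so meet the PP criterion. Doses of 27 and 28 move from 80-100% to above 100%.

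**Step 3: shorter courses, bracket corrected.** The inflation grows as the course shortens.
- Last dose on POD8 with 12 doses: 12/16 = 75.0% inclusive, 12/14 = 85.7% by date difference.
- Last dose on POD4 with 5 doses: 5/8 = 62.5% inclusive, 5/6 = 83.3% by date difference.
- One day only: the denominator is 2 on the inclusive count and 0 by date difference, so criterion (iii) cannot be evaluated.

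**Step 4: which count fits the rest of the SAP.**
- Table 2 calls POD1 to POD14 a 14-day course; the date difference is 13.
- The Section 11.1 duration bands run from 1 day to 14 or more. By date difference a full course falls in the 9-13 day band and a one-day user in none.
- The Section 11.1 dose bands treat 28 as the exact full course; the Section 9 denominator would be 26. A subject with 27 of 28 doses over POD1 to POD14 would be short of a full course in the exposure table and above 100% in the compliance table.
- Section 10.2.2.3 sets apart durations under 14 days. By date difference a complete course would literally meet that condition. No rescue count should change, because a rescue started more than two days after a POD14 last dose is already outside the 14-day treatment period.

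All four fit an inclusive count only.

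**The case against.** The strongest reply is that the intent is plain on both points. Parentheses around a single term make sense only if duration times 2 was meant as the denominator, and the bands make sense only on a 0-100 scale, so a score of 400% would be caught at the first tabulation. On the day count, the bands, together with references in Sections 6.3.5 and 7.1 to completing 14 days of dosing, already point to an inclusive count. PP exclusions are identified and documented before unmasking, and diary data are listed, so a wrong score could be seen. Some subjects with six or seven missed doses might also be excluded for major under-dosing deviations whatever their score.

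Much of this stands. It makes the 400% figure an unlikely output and the +1 point an ambiguity to close; it does not show that a date difference was intended. It does not make the printed rule correct, and review before unmasking is more likely to catch 400% than a full course at 107.7%.

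Two points of scope are also fair. The 21- and 22-dose result holds only for dosing that spans POD1 to POD14: a subject who stopped on POD11 with 21 or 22 doses scores 95.5% (21/22) or 100% (22/22) on the inclusive count and passes under either reading. And the compliance and exposure tables can differ even under a correct formula, because one is relative to actual duration and the other counts doses against 28; 21 correct doses over 10 inclusive days is 105%. The disagreement for a full-span subject with 27 doses, however, comes only from the missing +1.

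**Conclusion.** The concern holds. The bracket error is unconditional: the formula as printed cannot serve as the operative rule for PP criterion (iii), since 6 of 28 doses would satisfy it. The missing +1 is conditional on reading the rule as a date difference. On that reading, with the bracket corrected and dosing spanning POD1 to POD14, the effective minimum falls from 23 to 21 doses and a perfect course scores 107.7%. Shorter courses are inflated more, and a one-day user has no computable score.

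The consequence is limited to PP membership, and hence one sensitivity analysis of each primary endpoint, and to the compliance and exposure tables. The ITT primary analysis, alpha and sample size do not use this quantity; the 14-day thresholds in Section 6.3.5 refer to days of dosing, not to the Section 9 duration. The documents do not show how many subjects would fall at the affected dose counts. The correction should be made, but it does not threaten the main conclusion.

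**What to change.** In Section 9, replace the formula with: Compliance (%) = 100 x doses instilled correctly / [2 x (last dose date - first dose date + 1)]. Use the same inclusive duration, last dose date - first dose date + 1, in Section 11.1, and refer to it where Section 10.2.2.3 speaks of treatment duration.

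The cost is wording only: one bracket and one +1 in Section 9, the same +1 in Section 11.1, and a cross-reference in Section 10.2.2.3. No new data are needed, and neither the primary analysis nor the 80% PP policy changes. It should be in place before PP exclusions are decided, which Section 5.2 sets ahead of database lock and unmasking.

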10. EFFICACY ANALYSES

All efficacy analyses will be performed using the ITT population. In addition, analyses of the primary efficacy endpoints will be performed using the PP population as a sensitivity analysis. All efficacy analyses and summaries will be based on assessments in the study eye for each subject.

The data for subjects who are rescued at any time after the first dose of study drug and before the efficacy assessments at POD15 will be handled as described in [Sections 6.4.2](#) and [6.4.3.1](#). The data for subjects who prematurely discontinue the study without taking any rescue medications will be handled as described in [Section 6.4.3.1](#).

The Analysis Visits (PODs 4, 8 and 15) defined in [Section 6.3.5](#) will be employed in the efficacy analyses.

Baseline values for the efficacy endpoints are defined as the assessment values obtained at POD1 pre-dose.

All efficacy data will be presented in listings.

10.1 Analyses of Primary Efficacy Endpoints

10.1.1 Primary Efficacy Endpoints

The primary efficacy endpoints are:

- The proportion of subjects with ACC count = 0 (ACC grade = 0) at POD8, maintained through POD15
- The proportion of subjects with Ocular Pain grade = 0 at POD4, maintained through POD15

The ACC count will be graded as shown below:

Grade	0	1	2	3	4
ACC Count	0 cell	1-5 cells	6-15 cells	16-30 cells	> 30 cells

The subject-rated Ocular Pain will be graded as follow:

Grade	Description
0	None: No pain.
1	Minimal: Presence of minimal throbbing or aching pain (expected following cataract surgery).
2	Mild: Presence of mild throbbing or aching pain, easily tolerated.
3	Moderate: Presence of moderate throbbing or aching pain leading to the desire to use an analgesic.
4	Severe: Presence of severe throbbing or aching pain that is not tolerable

10.1.2 Primary Analysis

The Pearson's Chi-square test will be used to test the null hypothesis that there is no difference between treatment groups for the primary efficacy endpoints:

1. The proportion of subjects with ACC count = 0 (ACC grade = 0) at POD8, maintained through POD15
2. The proportion of subjects with Ocular Pain grade = 0 at POD4, maintained through POD15

Since the treatment comparisons of the primary efficacy endpoints are in sequential order, the fixed-sequence hierarchical testing approach will be used to adjust for multiple comparisons. The primary analysis will first compare the proportion of subjects with ACC count = 0 (ACC grade = 0) at POD8, maintained through POD15, between APP13007 and placebo. If the test is statistically significant at the 2-sided $\alpha = 0.05$ level in favor of APP13007, the comparison of the proportion of subjects with Ocular Pain grade = 0 at POD4, maintained through POD15, between APP13007 and placebo will be tested at the two-sided $\alpha = 0.05$ level.

Under the hierarchical testing scheme, once the two-sided p-value exceeds 0.05, the endpoint further down in the sequence will not be claimed for statistical significance.

The tabulated summary of the two endpoints will include the Responder (Response =Yes) and Non-responder (Response=No) for ACC count = 0 (ACC grade = 0) at POD8, maintained through POD15, or for Ocular Pain grade = 0 at POD4, maintained through POD15, and the 95% confidence interval (CI) for Responder. The treatment difference of the Responder rates with the associated 95% CI will be presented. The Response will be further categorized as:

Yes (Responder):

- Yes – Without imputed data
- Yes – With imputed data

No (Non-responder):

- No – With Rescue Medication Use
- No – Without Rescue Medication Use
- No – With imputed data

10.1.3 Sensitivity Analyses

Sensitivity analyses will be performed to confirm the robustness of the primary efficacy analysis results:

1. Analysis of the primary endpoints will be performed using the PP population.
2. “Completed-Case” analysis of the primary endpoints will be performed using the subgroup of Completers based on the ITT population. Completers are defined as the subjects who complete the study and have the data for the ACC count and ocular pain grade assessments at all visits up to POD15.
3. “Observed-Case” analysis of the primary endpoints will be performed using the ITT population and the observed data for subjects who discontinue prior to POD15 without taking rescue medication. The subjects with missing data will be considered as treatment failures (Non-responders).
4. “Worst-Case in the Analysis Window” analysis of the primary endpoints will be performed using the ITT population and using the worst Response at PODs 4, 8 and 15 when multiple efficacy assessments fall within the same analysis window for each Analysis Visit.
5. If more than 5% of data are missing for determining the primary efficacy endpoints in any treatment group, a tipping point analysis will be performed when the statistical significance of a treatment difference between two groups has been claimed for each of the two primary endpoints. Missing data for subjects who take a rescue medication will not be considered as ‘missing’ since the subjects will have been assigned as treatment failures (Non-responders).

The tipping point analysis of the primary endpoints will be performed using the ITT population to determine the number of subjects with imputed data in the placebo group whose response status has to be changed from Non-Responder to Responder in order to make the treatment difference between the two treatment groups no longer statistically significant.

10.1.4 Additional Analysis

The primary efficacy endpoints will be analyzed using the data collected up to POD15. The rescued subjects will not be considered as treatment failures (Non-responders) for this analysis. All subjects' data collected up to POD15, including the data from subjects who take rescue medication, will be used to analyze the primary efficacy endpoints. Only observed data will be included to derive the primary efficacy endpoints. For the primary endpoint of ACC grade, subjects who miss one of POD 8 and POD15 assessments will be considered as treatment failures (Non-responders). For the primary endpoint of ocular pain grade, subjects who miss one of PODs 4, 8 and 15 assessments will be considered as treatment failures (Non-responders). The Pearson's Chi-square test will be used to test the treatment difference.

